8.1.4 Treatment Planning Technique

The following normal tissues will be contoured on every slice of the CT scan. The bladder will include the portion inferior to the planning target volume. The rectum will include the portion inferior to the planning target volume and superior to the level that it leaves the posterior pelvis in the rectosigmoid transition. The small and large bowel will include at least 2 cm above the planning target volume. The femoral heads should be contoured to include the greater trochanter.

All patients on the dose escalation study will be treated using IMRT, which requires inverse treatment planning. This involves setting dose constraints on the IMRT treatment planning software.

The following dose constraints must be met for all plans:

1. Small bowel D2cc \leq 55 Gy
2. Large bowel (including the sigmoid) D2cc \leq 65 Gy
3. Rectum D10cc \leq 70Gy
4. Small bowel $<$ 10% to receive \geq 50 Gy
5. Bladder D10cc \leq 70 Gy
6. Spinal cord Dmax (maximum point dose) $<$ 45 Gy.
7. Individual Kidneys V18(volume receiving 18Gy or more) $<$ 33%

If constraints cannot be met after IMRT optimization, the PTV volumes may be reduced to meet criteria. These modifications will be recorded as part of the protocol to determine the feasibility of this approach.

The following dose constraints serve as ideal goals, however, coverage of the PTVs will be prioritized above these values, and modifications of volumes will not be performed to meet them. Plans exceeding the following constraints will not be protocol violations.

8. Femoral head D2cc $<$ 50 Gy
9. Femoral head \leq 15% to receive \geq 30 Gy
10. Sigmoid $<$ 20% to receive \geq 55 Gy
11. Sigmoid $<$ 50% to receive \geq 50 Gy
12. Rectum $<$ 20% to receive \geq 60Gy
13. Rectum $<$ 50% to receive \geq 50 Gy
14. Bladder $<$ 30% to receive \geq 60Gy

15. Bladder < 50% to receive ≥ 50 Gy

8.1.5 Radiation Dose Escalation Levels

This protocol will be using simultaneous, integrated boost using “dose painting” planning techniques. With this several volumes receive different daily doses. In general, the goal of this protocol is for the standard elective volumes to receive a fixed 1.8Gy per fraction, and for the boost volumes to receive higher doses per fraction to achieve the “boost” dose. All patients will receive a minimum of 45Gy in 25 fractions (i.e. 1.8 Gy per fraction) to the central disease (if intact uterus/cervix) and the elective nodal basins. The central disease will be boosted subsequent to this either by brachytherapy for further external beam as per the treating physicians preference, in accordance with the standard of care . Patients with parametrial or pelvic sidewall involvement will undergo an integrated boost to **PTV 55** as described above. In this setting, the IMRT plan will deliver 55 Gy in 25 fractions (2.2Gy per fraction) to **PTV 55**. This will be an integrated boost which occurs at the same time as the elective 45Gy (using dose painting treatment planning).

Patients will accrue to the following dose-escalation scenarios to treat **PTV boost** with an integrated boost (occurring at the same time as the above described plan, using dose painting treatment planning):

Dose level 1: 2.4 Gy X 25 fractions = 60 Gy

Dose level 2: 2.6 Gy X 25 fractions = 65 Gy

Dose level 3: 2.8 Gy x 25 fractions = 70 Gy

If the 2 dose limiting toxicities are dose level 1, therapy will be de-escalated to Dose level 0 defined below.

Dose level 0: 2.2 Gy X 25 fractions = 55 Gy

Patients will be set up daily using on-board imaging +/- cone-beam CT. Radiation will be given with 5 daily fractions per week, with exceptions made for dates in which the clinic is closed due to holiday or for linac maintenance.

The dose will be escalated in a 3X3 fashion, as defined below in **section 9.1.7** [14].

8.1.6 Dose Limiting Toxicities (DLTs)

The National Cancer Institute’s Common Terminology Criteria for Adverse Events (CTCAE), version 4.0 will be used to score and grade treatment-related toxicity.

Two distinct toxicities are to be considered in this protocol: acute and late. These types of toxicity are distinct in terms of time of onset, character, management, and expected course, thus they will be considered separately for the purposes of determining the MTD.

Since integrated radiation dose escalation is unlikely to substantially affect the hematopoietic system, only non-hematologic, grade 3-4, acute toxicity will be considered the primary dose-limiting toxicity (acute DLT).

Acute DLT will be defined based on the side effects inherent from radiation therapy for gynecologic cancers, including effects on bowel, bladder, and skin. Dose limiting toxicity will include any of the following during treatment or within 6 weeks of completion:

1. Acute Grade 3-4 enteritis or proctitis requiring:
 - a. Tube feedings
 - b. Total parenteral nutrition
 - c. Hospitalization secondary to inadequate oral caloric or fluid intake
 - d. Prolonged treatment breaks secondary to enteritis (> 1 week)

e. Life-threatening consequences such as bowel perforation, obstruction, or bleeding requiring transfusion.

2. Acute Grade 3-4 bladder toxicity
 - a. Bladder ulceration or necrosis
 - b. Grade 3-4 cystitis including hematuria requiring transfusion
 - c. Urinary obstruction not due to clot passage
3. Grade 4 dermatologic toxicity (skin necrosis or ulceration of full thickness of dermis)

Late DLTs will be defined at grade 3-4 GI or GU toxicity with onset after 6 weeks of treatment. The CTCAE v 4.0 will be used for determination of late toxicity grade, with one exception: the use of plasma coagulation or similar procedure for rectal bleeding will not be considered a late DLT, even though it is considered a grade 4 toxicity by the CTCAE. If however, there are other consequences of radiation proctitis which meeting grade 3-5 criteria, this will be considered a late DLT.

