8.1.7 Dose Escalation Schema

Dose escalation will operate in the following fashion based on acute DLTs:

1. 3 patients will be accrued to dose level X (starting at level 1)
2. If there are any acute DLTs noted in these initial three participants, and additional three will be accrued (for a total of six).
3. If there is a second acute DLT, accrual will be halted for that cohort, and the dose will be deescalated to level X-1.
4. If 0/3 or 1/6 participants have an acute DLT, after a minimum follow up of 6 weeks, accrual to cohort X+1 may begin.
5. The candidate cohort for MTD will accrue a total of 6 patients. Thus if the dose deescalates, the dose cohort X-1 must have 6 participants before declaration of MTD. Similarly if the protocol proceeds to level 3, then it will accrue 6 participants even if no patient has an acute DLT.

The following schema will be used for late DLTs in conjunction with the above acute rules:

1. Patients will be monitored for late toxicity at every follow-up for 3 years.
2. If a late DLT observed in cohort Y, accrual in that and any higher cohort will be held until there is a minimum of 3 month follow up for all patients.
3. If a second late DLT is observed in cohort Y, then the dose will be de-escalated to Y-1 as per the above schema.
4. If there are no additional late DLTs in cohort Y, then a total of 6 patients must accrue to cohort Y, with a minimum of 3 months follow-up with no further late DLTs before the dose may be escalated to, or for accrual to resume in cohort Y+1.

Of note, acute and late DLTs will be counted separately. Thus if a patient has both an acute DLT and a late DLT, they will be counted as 1 DLT for both schema. If a patient has an acute DLT but not a late DLT, they will only be counted in the acute schema. The only exception will be a patient has an acute

DLT which does not resolve to less than grade 2 by 3 months: these will be counted as both acute and late toxicity for determination of MTD.

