8.1.8 Treatment Interruptions during RT

The majority of RT-induced side effects requiring treatment breaks will be gastrointestinal in nature and include nausea/vomiting, weight loss, and dehydration. Dietary adjustments, anti-emetic therapy will be pursued. Treatment breaks due to enteritis/proctitis will be given at the discretion of the radiation oncologist. Other reasons for a treatment break will be:

1. Neutropenia with ANC < 500
2. Thrombocytopenia with platelets < 10,000
3. Non-hematologic grade 3-4 toxicity if felt by treating radiation oncologist that a break is necessary (i.e. significant skin reaction).

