10.0 RISKS/BENEFIT ASSESSMENT

Patients with locally-advanced gynecologic cancers are at high risk of relapse and death. Long-term (3-4 years) survival is ~30-40% in patients with good performance status. Local failure after concurrent chemotherapy and radiation therapy occurs in ~40-50% of patients. Thus, increasing the intensity of RT is rational and may improve clinical outcomes for these patients.

The expected acute side effects of RT to the pelvis include fatigue, skin erythema, enteritis, proctitis, and cystitis. The incidence of acute grade 3-4 enteritis / proctitis with conventional therapy is 20-35% of

patients, while that of hematologic toxicity is 20-40% and cystitis is 5%. It is possible that the risk of severe enteritis / proctitis (requiring treatment breaks, intravenous fluids, hospitalization, etc.) will be greater with increased radiation boost dose. We will attempt to avoid this by utilizing IMRT, which can better spare normal tissues from the high dose component of treatment. In addition, it is possible that the use of IMRT (which can potentially increase the volume of normal tissues getting a low dose of RT) will increase the risk of acute side effects. The patients will be monitored weekly during RT and regularly after treatment to evaluate these toxicities and determine the maximum tolerated dose.

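### Acute DLT item 1 covers enteritis or proctitis, but sub-item 1d counts a break of over 1 week only when enteritis caused it: probably a drafting slip, and worth closing

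*Combined protocol and SAP*

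**What the plan says.** Section 8.1.6 lists the acute DLTs that apply during treatment and for 6 weeks after it. Item 1 is headed "Acute Grade 3-4 enteritis or proctitis requiring", followed by five sub-items: (a) tube feeding, (b) parenteral nutrition, (c) admission for poor intake, (d) a treatment break, and (e) life-threatening bowel events. Sub-item 1d reads "Prolonged treatment breaks secondary to enteritis (> 1 week"; it names the cause again and leaves proctitis out.

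Section 8.1.7 turns the count into decisions: "If 0/3 or 1/6 participants have an acute DLT, after a minimum follow up of 6 weeks, accrual to cohort X+1 may begin", and "If there is a second acute DLT, accrual will be halted for that cohort, and the dose will be deescalated to level X-1".

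Elsewhere the protocol treats the two conditions together as causes of breaks. Section 8.1.8 says "Treatment breaks due to enteritis/proctitis will be given at the discretion of the radiation oncologist". Section 10 says it is possible that "the risk of severe enteritis / proctitis (requiring treatment breaks, intravenous fluids, hospitalization, etc.) will be greater with increased radiation boost dose".

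**The concern.** Sub-item 1d is part of the rule that drives escalation, so its wording decides who is counted. If a patient stops radiation for more than a week because of severe proctitis and meets no other sub-item, the literal text leaves that patient out. A cohort with 1/3 would then read as 0/3 and escalate without expanding to six. A cohort with 2/6 would read as 1/6 and escalate where the rule calls for a halt and de-escalation. Either error runs toward a higher dose.

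Section 10 names severe enteritis or proctitis needing treatment breaks as a risk that may rise with boost dose. An event of that kind should not depend on how one reader takes one word.

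**Working it through.** **Step 1: which rule could count the event.** Take a patient with grade 3-4 proctitis and no contributing enteritis, a break of more than 1 week, no feeding support, no admission for poor intake and no life-threatening bowel event.

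| Rule | Counts the event? | Reason |
|---|---|---|
| 8.1.6, items 1a-1c | No | Need tube feeding, parenteral nutrition or admission for poor intake |
| 8.1.6, item 1d | Not literally | The break must be due to enteritis |
| 8.1.6, item 1e | No | Needs a life-threatening consequence |
| 8.1.6, items 2 and 3 | No | Bladder and skin only |
| 8.1.6, late DLT | No | "Late DLTs will be defined at grade 3-4 GI or GU toxicity with onset after 6 weeks of treatment" |
| 8.1.7, 3-month carry-over | No | Applies to an acute "DLT which does not resolve to less than grade 2 by 3 months", so an acute DLT must already have been scored |
| Section 11, 4-week cut-off | Possibly | Calls toxicity after 4 weeks late, and the late definition takes any grade 3-4 GI toxicity |

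The last row conflicts with the 6-week boundary in 8.1.6. The course is 25 fractions at 5 per week, which is 5 weeks. Under Section 11, proctitis starting in the first 4 weeks of treatment is still early and falls back on 1d. Only later onset could be counted as late. Even then it enters the separate late schema, which holds accrual after a first event; it is not added to the acute count.

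**Step 2: the plan's own figure.** The maximum sample size in Section 11 is 6 × 4 = 24. It reproduces, and rewording 1d does not change it.

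**Step 3: illustration of the effect on a decision.** Let p be the chance per patient of a DLT that is listed on the literal reading, and g the chance of a proctitis-only break over 1 week with no listed DLT. The documents give neither. The nearest figure is the combined 20-35% for acute grade 3-4 enteritis or proctitis with conventional therapy (Section 10), which separates neither proctitis nor breaks. Both p and g are therefore assumed. The calculation also assumes independent patients, ignores the late schema, and applies the literal reading every time.

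- Chance of at least one such event among six patients: 1 − (1 − g)^6. For g = 1%, 2%, 5% this is 5.9%, 11.4%, 26.5%.
- Chance that a level passes at 0/3 or 1/6: f(p) = (1 − p)^3 + 3p(1 − p)^5.
- Counting extra events can turn a pass into a stop but never the reverse. The chance that the two readings disagree is therefore f(p) − f(p + g).

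At p = 0.20:

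- f(0.20) = 0.51200 + 0.19661 = 0.7086
- f(0.22) = 0.47455 + 0.19055 = 0.6651, difference 0.0435
- f(0.25) = 0.42188 + 0.17798 = 0.5999, difference 0.1088

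| Assumed p | g = 1% | g = 2% | g = 5% |
|---|---|---|---|
| 10% | 1.7% | 3.5% | 9.2% |
| 20% | 2.2% | 4.4% | 10.9% |
| 33% | 1.9% | 3.8% | 9.2% |

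The formula fits levels that can pass on three patients. Level 3 and any candidate MTD level take six regardless. There the chance of two or more DLTs in six at p = 0.20 is 0.345. It rises to 0.394 for g = 2% and 0.466 for g = 5%, differences of 0.049 and 0.121. The order of size is the same.

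**The case against.** The best answer is that a sensible reader would already count the event. Sub-item 1d sits under a heading that names both conditions, so *enteritis* there may be shorthand for the pair. The list is introduced with open wording, and the paragraph before it speaks of non-hematologic grade 3-4 acute toxicity in general. The group is also very narrow. Section 8.1.8 describes the usual causes of breaks as nausea, weight loss and dehydration, which is not a picture of isolated proctitis. The planning rules lower the risk further: the rectum is held to D10cc ≤ 70 Gy, and in cohorts 2 and 3 the large bowel, including the rectum, may be cut from the boost volume. Escalation is permitted and not automatic, and Section 11 tabulates all toxicities by type and grade, so the event would be visible.

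Most of this stands, and it is why the point is minor. Two parts do not settle the matter. The general sentence cannot replace the list, because the list narrows it: item 3 accepts only grade 4 skin toxicity. And open wording leaves the call to judgement after the event, in a cohort of three to six, which a DLT definition is meant to avoid.

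A reader might go further and infer that proctitis breaks were deliberately excluded, or that no rule in the protocol could ever count them. The documents support neither. The heading, 8.1.8 and Section 10 argue against intent, and the Section 11 cut-off could bring in events that start after week 4.

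**Conclusion.** The mismatch between the item 1 heading and 1d is real and sits in an operative rule. On the literal text, a break of over 1 week from grade 3-4 proctitis alone is not a listed acute DLT, and onset in the first 4 weeks is not caught by any other rule. It is most likely a drafting slip.

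The practical effect is small and cannot be quantified from the documents. A reader might take the percentages above as an error rate for this trial, or conclude that the MTD will be set too high. Neither follows: p and g are assumptions, and the figures suppose a literal reading that the rest of the protocol suggests was not meant. What does hold without any assumed rate is that the 0/3 and 1/6 limits turn on a single patient, so one uncounted event is enough to change a decision. This is a point for the sponsor to consider, not a flaw in the design.

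**What to change.** In 8.1.6, item 1d, insert *or proctitis* after *enteritis*, keeping the limit of more than 1 week. This aligns 1d with its own heading, with 8.1.8 and with Section 10. It takes two words, adds no assessments and leaves the maximum sample size at 24. The downside is that slightly more events may count as DLTs, so a level may expand or stop a little more often. That is the cautious direction for patients.

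### Grade 3 bowel toxicity that starts in the acute window, meets no listed acute DLT criterion and persists is counted in neither the acute nor the late DLT schema

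*Combined protocol and SAP*

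**What the plan says.** Three rules in the combined protocol and SAP decide whether a bowel or bladder event counts.

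- **Acute DLT (Section 8.1.6).** The window is set by "Dose limiting toxicity will include any of the following during treatment or within 6 weeks of completion". The bowel item opens "Acute Grade 3-4 enteritis or proctitis requiring" and then lists five consequences, a to e: tube feeding, parenteral nutrition, admission for poor intake, a break of more than a week for enteritis, or a life-threatening complication. Grade alone is not enough. The bladder item is wider: 2b is "Grade 3-4 cystitis including hematuria requiring transfusion", with no further consequence required.
- **Late DLT (Section 8.1.6).** "Late DLTs will be defined at grade 3-4 GI or GU toxicity with onset after 6 weeks of treatment". The classifier is onset, not the grade present at a later visit.
- **Carry-over (Section 8.1.7).** Acute and late DLTs are counted separately. One exception is allowed, and it presupposes that the patient already had an acute event on the list. It covers a "DLT which does not resolve to less than grade 2 by 3 months: these will be counted as both acute and late toxicity".

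Section 11.0 restates the split differently: early toxicities occur in the first 4 weeks of treatment and late ones after 4 weeks.

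**The concern.** The maximum tolerated dose is the primary objective, and the late schema can act on it alone: a first late DLT holds accrual in that cohort and any higher one, and a second de-escalates. The carry-over sentence shows that the authors wanted unresolved toxicity to reach the late count. It does so only for patients who already had an acute DLT.

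A patient with continuous grade 3 bowel toxicity that never triggered a to e has no route into either count. Staff who apply the text exactly would leave that patient out, since Section 8.1.6 separates acute from late partly by time of onset and Section 9.3 requires the onset date to be recorded. A level could then be passed with more chronic severe bowel toxicity than the rule is meant to allow.

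**Working it through.** The point concerns definitions, so the main check traces events through the rules. The one design figure in Section 11.0, a maximum of 6 x 4 = 24 patients, reproduces and is unaffected.

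**Step 1: trace the events.**

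| Event | Acute DLT? | Late DLT? | Carry-over? | Counted in |
|---|---|---|---|---|
| Grade 3 enteritis from week 4 of RT, none of a-e, still grade 3 at 3 months | No, no a-e item | No, onset too early | No, no acute DLT to carry | Neither |
| Grade 3 GI event not classed as enteritis or proctitis, same course | No, not on the list | No, onset too early | No | Neither |
| Grade 3 cystitis from week 4, persisting | Yes, item 2b | Only through carry-over | Yes | Both |
| GU grade 3 event outside 2a-2c (for example clot obstruction, given that 2c is "Urinary obstruction not due to clot passage"), persisting | No | No, onset too early | No | Possibly neither |
| Grade 1-2 early, first grade 3 after the boundary | No | Naturally read as yes | Not needed | Late |

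**Step 2: does the gap depend on where the boundary lies?** Section 8.1.5 gives 25 fractions at 5 per week, so 25/5 = 5 weeks of external beam without interruption. Brachytherapy or breaks would lengthen this. Measured from the start of radiotherapy:

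| Reading of the boundary | Late begins | Early-onset period exposed to the gap |
|---|---|---|
| Section 8.1.6, 6 weeks from completion | 5 + 6 = week 11 | Weeks 0-11 |
| Section 8.1.6, 6 weeks from start | Week 6 | Weeks 0-6 |
| Section 11.0, 4 weeks | Week 4 | Weeks 0-4 |

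The reading changes the width of the gap. None of the three removes it for events that start in the first weeks of treatment.

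**Step 3: is such an event plausible on the documents' own terms?** Section 10.0 puts acute grade 3-4 enteritis or proctitis at 20-35% with conventional therapy. Section 8.1.8 leaves breaks for enteritis or proctitis to discretion, and only breaks over one week meet item d. Appendix B lists grade 3 large-bowel findings outside a to e, such as discharge that needs pads. Appendix B is the RTOG scale and DLTs are graded by CTCAE v4.0, so this is indicative only. The documents do not say what share of grade 3 events meets none of a to e, or how many persist.

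**Step 4: direction and leverage.** Take six patients with one counted late DLT and one uncounted persistent grade 3 event. The count is 1, so the level is not de-escalated under 8.1.7; with both counted it is 2, and it is.

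To illustrate direction only, let r be the true late grade 3-4 GI rate and f the share uncounted. The counted rate is p = r(1 - f), and P(at least 2 of 6) = 1 - (1-p)^6 - 6p(1-p)^5. The values of r are the late GI rates in Table 1; f is an assumption.

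| r | f = 0 | f = 25% | f = 50% | f = 75% |
|---|---|---|---|---|
| 10% | 0.114 | 0.069 | 0.033 | 0.009 |
| 14% | 0.200 | 0.124 | 0.061 | 0.017 |
| 34% | 0.662 | 0.478 | 0.271 | 0.086 |

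Example: r = 14%, f = 50% gives p = 0.07 and P = 0.061. The probability rises with p, so any f above zero lowers it. These are not operating characteristics of the design: f is assumed, the rates come from other regimens at 2 to 4 years of follow-up, and n is fixed at 6 although a level may pass at 0/3.

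**The case against.** The strongest reply is that other text closes the gap.

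- **The general sentence.** Section 8.1.6 says "only non-hematologic, grade 3-4, acute toxicity will be considered the primary dose-limiting toxicity (acute DLT"), and the list is introduced as what DLT will include. Read broadly, every non-hematologic grade 3-4 acute event is a DLT and carry-over then works. But the condition attached to the bowel item and the grade-4-only skin item would have no function. The restrictive reading is the stronger one. If the broad one is intended, the list contradicts it and needs correcting.
- **The proctitis sentence.** After exempting coagulation for rectal bleeding, 8.1.6 says that other grade 3-5 consequences of radiation proctitis are late DLTs, and it repeats no onset condition. Persistent grade 3 proctitis is therefore arguably covered. The sentence qualifies a definition that rests on onset, however, and it does not reach enteritis.
- **Section 11.0.** Under its 4-week split, enteritis that starts in week 5 is late. That stands: the gap is certain across all readings only for earlier onset.

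A reader might also infer three stronger points that the documents do not support. Bladder toxicity in general does not escape, because item 2b captures grade 3-4 cystitis and carry-over follows. Toxicity that starts at grade 2 and first reaches grade 3 after the boundary is naturally read as a late DLT. Nor do the rules simply count persistent grade 2 and omit persistent grade 3: the grade 2 case concerns a patient who already had an acute DLT, and such a patient still at grade 3 is counted too.

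**Conclusion.** The gap is real and narrow. As written, grade 3 bowel toxicity (and a few GU events outside 2a-2c) that begins in the acute window, meets no listed acute criterion and persists at grade 3 past the boundary falls outside both schemas. This rests on the restrictive reading of the acute list and on onset meaning the start of the toxicity; the proctitis sentence may rescue part of it.

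The direction is certain, since omitting events can only make a level look safer, and in a cohort of six a single event can change the decision. The size is not known. It would be tempting to infer a definite upward bias in the MTD from the illustrative probabilities, but they depend on an uncounted share that no document supplies. The point still warrants correction because the affected count sets the primary endpoint and the remedy is cheap.

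**What to change.** Reconcile Sections 8.1.6, 8.1.7 and 11.0:

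1. Give one acute/late boundary in place of the 6-week and 4-week versions, and say whether it runs from the start or the completion of treatment, and of which treatment.
2. Say whether the acute list is exhaustive, so that it agrees with the general sentence before it.
3. State how grade 3-4 GI or GU toxicity is counted when it starts in the acute window, is not an acute DLT and is still present after the boundary, so that it cannot fall outside both schemas by default. Align the carry-over exception with that statement. Which rule to adopt is for the sponsor.

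This should be settled before cohorts are judged; deciding case by case after events are known would undermine the MTD determination. The cost is a wording amendment. Toxicity is already assessed at follow-up (Section 9.1) and onset dates are already recorded (Section 9.3), so no visits, data items or patients are added. If these events are counted, accrual holds or de-escalation may occur slightly more often.
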